The physical function sub-score of PF-10, role limitations due to physical problems, will be a key secondary endpoint of SARA-INT. PF-10 has been tested in numerous clinical trials and is considered a simple and effective measure of mobility disability and is also often used in epidemiological studies (Syddall, 2009³⁵). Climbing one flight of stairs (no change versus decline of two levels) with a 2-point difference) or walking a block (no change versus two levels decline) exemplifies a substantial meaningful change, as appreciated by patients (Perera, 2006³⁶).

In SARA-INT, SF-36 will be auto-administered, either electronically or by filling out a paper booklet manually as provided by the clinical center .

Pepper Assessment Tool for Disability (PAT-D)

The Pepper Assessment Tool for Disability (PAT-D) is a disability questionnaire that was developed to assess difficulty with functioning in both discrete tasks and social/role functioning. The PAT-D has been widely used in randomized controlled trials and observational studies in a variety of chronic health conditions⁵⁸. There are three domains: mobility, activities of daily living, and instrumental activities of daily living. This questionnaire asks respondents how much difficulty they have had with a range of activities in the past month due to their health. For each item, respondents answer on a 5-point Likert-type scale whether they experience: (1) no difficulty, (2) a little difficulty, (3) some difficulty, (4) a lot of difficulty, or (5) unable to do. For each item there is also a 'not applicable' option if the respondent usually did not do that activity for reasons other than disability. The PAT-D produces a score for each of the three domains as well as a total score, with higher scores indicating greater disability.

This questionnaire will be administered by the clinical center personnel at Day 0 and M6.

Sarcopenia Quality of Life (SarQoL)

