The SarQoL is a sarcopenia-specific, self-administered, quality of life questionnaire designed for community-dwelling elderly study participants aged 65 years and older⁵⁹. The questionnaire will be provided to study participants in the appropriate language. The questionnaire contains 22 questions, which takes approximately 10 minutes to complete. The questionnaire covers 7 domains: physical and mental health; locomotion; body composition; functionality; activities of daily living; leisure activities; and fears. Most questions are answered on a 4 point Likert scale.

This questionnaire will be auto-administered, electronically or filling a paper booklet provided at the clinical centre.

Test SIO Disabilità Obesità Correlata (TSD-OC)

The TSD-OC is considered a reliable and valid instrument for measuring self-reported disability in obese subjects⁶⁰. The questionnaire is a set of multiple questions in 7 dimensions to measure pain; stiffness; function and autonomy in daily activities, housework, outdoor activities, occupational activities, and social life. Each question is scored by the subject from 0 (best) to 10 (worst). Each dimension score is calculated and then all dimension scores are added together for a total TSD-OC score.

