4.2 Secondary endpoints

The key secondary endpoints of this study are:

- Change from baseline to M6/M9 in Physical Function Domain (PF-10) sub-score of the Short Form Health Survey (SF-36)
- Change from baseline to M6/M9 in Handgrip strength test

The other secondary endpoints of this study are:

- Change from baseline of ALM and other parameters of body composition based on DEXA
 measurements
- The rate of success to complete 400 meter walking test after the 6-month/9-month treatment versus placebo
- Change from baseline of the distance during 6 Minute Walking Test (6MWT) distance
- Change from baseline in muscle strength based on the knee extension and the SCPT
- Change from baseline of the SPPB total score
- Change from baseline of the time for five chair stands as part of the SPPB assessment
- Change from baseline using the SarQol auto-evaluation questionnaire
- Change from baseline in PAT-D.
- Change from baseline in TSD-OC for obese patient
- Change from baseline in SF36 (total score)

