6.2 Full Analysis Set (FAS)

The FAS consists of randomized subjects, excluding subjects who failed to take at least one dose of trial medication and had a very early withdrawal (first week after randomization) definitely not related to study medication and lacked any post randomization data (CPMP/ICH/363/96). Subjects are included in the analysis using the FAS according to the treatment to which they were randomized.

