8.7.3.2 Analysis of other secondary efficacy endpoints

The other secondary endpoints will be analyzed using the FAS only.

Observed and change from baseline values for the following secondary efficacy endpoints will be summarized using descriptive statistics by treatment group. These endpoints will be analyzed using an ANCOVA method as defined in Section 8.7.1.12. This analysis will be performed without any correction for multiplicity.

- Change from baseline in ALM and other parameters of body composition by DEXA: The DEXA parameters will be ALM, ALM BMI, percentage lean mass for left/right arm, trunk and left/right leg and percentage fat mass for trunk, right/left leg and right/left arms.
- Change from baseline in muscle strength (knee extension) and stair climb power test (SCPT):

Knee extension will be performed at Day 0 and at the M6/M9 visit or the end-of-intervention visit and is measured using the maximum peak torque measurement (Nm) for 60°/s, 90°/s and 180°/s for the tested leg (either right or left). It is usually measured as the force applied to the ankle with the subject seated in an adjustable straight-back chair, the lower leg unsupported and the knee flexed to 90°. Knee extension will be measured 3 times for the chosen leg. The highest of all 3 attempts will be used for the summary and analysis. The assay with the highest torque output (highest value) will be taken for analyses.

The SCPT will be performed at Day 0 and at the M6/M9 visit and is the measure of ability to ascend and descend stairs which tests the body strength and balance. SCPT measures the time (in seconds) taken to ascend and descend a flight of stairs (10 steps with a 20cm step height). Step heights should be suitable (between 16 and 20 cm).

• Change from baseline in Pepper Assessment Tool for Disability (PAT-D) for obese patient.

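### SAP 8.7.3.2 attaches an obesity restriction to the PAT-D analysis that contradicts SAP 4.2, the section's own FAS rule and the protocol (minor; wrong as written)

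*SAP*

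**What the plan says.** SAP 4.2 lists "Change from baseline in PAT-D" among the other secondary endpoints, with no population limit. The next bullet is "Change from baseline in TSD-OC for obese patient", the only entry in that list restricted to obese participants.

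SAP 8.7.3.2 opens with "The other secondary endpoints will be analyzed using the FAS only". Under the endpoints to be analysed by ANCOVA it then gives "Change from baseline in Pepper Assessment Tool for Disability (PAT-D) for obese patient". Later in the same section, under the MMRM endpoints, TSD-OC carries the same limit.

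SAP 6.2 defines the analysis set: "The FAS consists of randomized subjects, excluding subjects who failed to take at least one dose of trial medication", with further conditions on very early withdrawal and absence of post-randomisation data. None of these concerns obesity.

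In the protocol, section 3 names PAT-D together with SarQoL and TSD-OC as other secondary endpoints and limits none of them to obese participants. Section 8.1 says of PAT-D: "This questionnaire will be administered by the clinical center personnel at Day 0 and M6".

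**The concern.** The bullet sits in the part of the SAP from which the analysis will be programmed, and it is the most specific statement about the PAT-D population. A programmer who follows it has to build a subset that no other text on PAT-D calls for, using a term the SAP does not define for this purpose. The nearest definition, in SAP 8.9.1, is the body-fat criterion for the sarcopenic-obesity subgroup (above 25% in men, above 35% in women), and nothing links it to PAT-D. A body-fat rule, a BMI cut-off and ignoring the phrase would each give a different sample, and the SAP does not say which applies.

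At stake is the precision and interpretability of one supportive outcome covering mobility and daily-living disability. It is also one of the four questionnaires that continued to be collected while on-site testing was suspended for COVID-19 (Protocol 2.2 and 4.2; SAP 3.1), so a literal reading would set aside data the trial went on gathering.

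**Working it through.** **1. What each source says about the PAT-D population**

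| Source | Obesity condition on PAT-D? |
|---|---|
| SAP 4.2, endpoint list | None |
| SAP 8.7, general text | Refers to section 4 for endpoint definitions |
| SAP 8.7.3.2, opening sentence | None; FAS |
| SAP 6.2, FAS definition | None |
| SAP 8.5.2, baseline summary | None; PAT-D domains and total summarised for the FAS |
| SAP 8.7.3.2, descriptive text under the PAT-D bullet | None |
| SAP Appendix D, scoring | None |
| Protocol 3, endpoint table | None |
| Protocol 1.3, schedule of activities | None |
| Protocol 8.1, instrument description | None |
| **SAP 8.7.3.2, PAT-D bullet title** | **Yes** |

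The bullet title stands alone. The SAP's section on changes to the planned analysis lists several departures from the protocol, and this is not one of them.

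**2. Which instrument is obesity-specific**

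Protocol 8.1 says of PAT-D: "The PAT-D has been widely used in randomized controlled trials and observational studies in a variety of chronic health conditions". Of TSD-OC it says: "The TSD-OC is considered a reliable and valid instrument for measuring self-reported disability in obese subjects". The limit therefore has a rationale for TSD-OC and none for PAT-D. A phrase carried over from the TSD-OC entry is the likely cause, but that is an inference; the contradiction stands whatever the cause.

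**3. Size if the bullet is followed literally**

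The documents give no sample size, standard deviation or target difference for PAT-D, so there is no planned figure to reproduce. Only relative precision can be shown.

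With n per arm and common standard deviation s, the standard error of a difference between two arms is s × sqrt(2/n). Keeping a fraction f of each arm gives s × sqrt(2/(f × n)). The ratio is 1/sqrt(f). This assumes the same variance in obese participants as in the whole set, and the same f in each arm.

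For scale, Protocol 9.2 plans 64 evaluable participants per arm, 3 × 64 = 192 in all. The values of f are assumptions.

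| f (assumed) | Kept of 192 | Kept per arm | CI width factor, 1/sqrt(f) |
|---|---|---|---|
| 0.8 | 154 | 51 | 1.12 |
| 0.6 | 115 | 38 | 1.29 |
| 0.5 | 96 | 32 | 1.41 |
| 0.3 | 58 | 19 | 1.83 |

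The documents cannot narrow f. Protocol 2.1 cites a prevalence of sarcopenic obesity of 4–84% in men and 4–94% in women, depending on how body composition is measured.

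**The case against.** The strongest reply is that the SAP already resolves the matter. SAP 8.7 sends the reader to section 4 for endpoint definitions, section 4.2 has no restriction, and 8.7.3.2 opens by assigning these endpoints to the FAS. A careful statistician would probably analyse PAT-D in the full FAS. This largely stands: it makes the problem an internal contradiction with most of the text on one side, and a reader who infers that the SAP as a whole excludes non-obese participants goes too far. What remains is that the specific bullet conflicts with the general text, and a SAP should not leave the analysed population to interpretation.

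Three other inferences are tempting and not supported:

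- **That the subset is post hoc.** It is written into a SAP that is to be signed off before database lock and unblinding (SAP 1). It is undefined and unjustified, but it is not post hoc.
- **That a stated secondary objective would go unanswered.** No objective names PAT-D. The related objective concerns sarcopenia-specific patient-reported outcomes, and SarQoL is analysed without an obesity limit.
- **That the protocol itself restricts TSD-OC to obese participants, so only PAT-D is out of line.** Protocol 3 and the schedule of activities put no such condition on TSD-OC. Protocol 8.1 only describes the population in which the instrument is considered valid. The TSD-OC limit appears only in the SAP, and its list of changes does not record it.

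**Conclusion.** The PAT-D bullet in SAP 8.7.3.2 is wrong as written, and the severity is minor. It contradicts the governing endpoint definition, its own section's population statement and the protocol, and it relies on an undefined term.

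Followed literally, it would widen the PAT-D confidence interval by 1/sqrt(f). No single figure for the loss can be defended, because f is not given; the tabulated factors are illustrations and rest on equal variance and an equal obese share across arms.

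The consequence is confined to PAT-D, a non-key secondary endpoint that SAP 8.7.1.6 treats as supportive and leaves without multiplicity adjustment. No primary or key secondary result depends on it.

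**What to change.** Delete the last three words of the PAT-D bullet in SAP 8.7.3.2, so that the ANCOVA uses the full FAS in line with SAP 4.2, the section's opening sentence and the protocol. This costs a three-word edit and needs no new data or derivation.

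Separately, settle TSD-OC in SAP 4.2 and 8.7.3.2. Either remove the limit there too, or keep it, define *obese* for that analysis (variable, cut-off and visit) and record it among the changes from the protocol. This costs one decision and, if the limit is kept, a definition and one line in the change list.

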8.7.5 Analysis of other efficacy datas

All other efficacy data described here will be summarized using the FAS.

Descriptive statistics of the observed scores and change from baseline by treatment group for each scheduled visit will be provided.

- Time to walk 400m, 200m, 100m
- SF-36: 8 subscales and two summary scores. The 8 subscales are: physical functioning, role limitations due to physical problems, bodily pain, general health perceptions, vitality, social functioning, role-limitations due to emotional problems, and mental health. The two summary scores are the physical component summary and the mental component summary. Each scale is directly transformed into a 0-100 scale on the assumption that each question carries equal weight. The lower the score, the more disability; the higher the score the, less disability (i.e., a score of zero is equivalent to maximum disability and a score of 100 is equivalent to no disability).

By-subject listings of other efficacy data will also be provided.

8.7.6 Impact of the COVID-19 Outbreak

Due to the COVID-19 outbreak, an updated strategy for the final analysis will be implemented, to account for the missing data on safety and efficacy which will have impact on the final analysis. This will include sensitivity analyses comprising before/after COVID_19 outbreak.

Subjects will be classified into two COVID-19 outbreak classification, including:

- 1. End of Study before 16MAR2020
- 2. End of Study after 16MAR2020

End of study date will be used in determining the COVID-19 outbreak classification, the last contact date will be used if no end of study date is available.

The COVID-19 outbreak classification will be calculated for primary endpoint and key secondary endpoints by using FAS population and PP population. The COVID-19 outbreak classification will be calculated for adverse events by safety population including all AEs, all TEAEs, treatment related TEAEs, treatment related Serious TEAEs, TEAEs leading to treatment discontinuation, serious

Page 40 of 69

AEs/TEAEs, Adverse events of special interest (AESI), Serious Adverse events of special interest (AESI), Treatment related Adverse events of special interest (AESI), and TEAEs leading to death by system organ class and preferred term.

8.7.6.1 Sensitivity Analyses of Missing data by Using Bayesian Multiple Imputation (MI) Methods

Bayesian MI method will be used to impute 400-m gait speed for the non-completers. The technical details of the Bayesian MI method have been described in publication¹⁰. Briefly, assumed that the 400-m gait speed data collected at 3, 6/ 9 months followed a multivariate normal distribution. The 400-m gait speed for the non-completers was imputed subject to the constraint that the value is less than 0.44 m/s. All imputations were performed separately for the two intervention groups. The SAS macro used to implement the procedure is detailed in Supplementary Appendix S1.

Two different Bayesian imputation models were used. The unadjusted Bayesian imputation model relied solely on the assumption that the 400-m gait speed of the non-completers was left-censored. . Non-completers include subjects who did not complete the test and discontinued from study, including discontinued due to COVID-19. The adjusted Bayesian imputation model used the baseline 400-m gait speed as a covariate in the imputation process.

Subsequently, we conducted analyses for the longitudinal 400-m gait speed data using both the simplistic imputation and the Bayesian MI methods. For the Bayesian MI method, analyses were performed on each of the 25 multiply imputed datasets obtained from the adjusted Bayesian imputation models. The results were then combined using Rubin's method carried out in SAS PROC MIANALYZE for valid statistical inference¹¹. In all analyses, linear mixed-effects models were fit with unstructured variance-covariance matrices. The models contained main effects for intervention assignment and visit and the intervention by visit interaction. Baseline 400-m gait speed was used as a covariate. Least square means were estimated for each intervention group at each follow-up visit. An example of the SAS program is included in Supplementary Appendix S2.

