8.7.1 Analysis methods

Treatment group comparison (175 mg BIO101 Vs Placebo and 350 mg BIO101 Vs Placebo) will be tested at a significance level of 0.05, 2-sided unless stated otherwise.

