Appendix S1 - A SAS macro for Implementing the Bayesian Multiple Imputation Method

Program: impute car only data.sas Purpose: Bayesian MI method for left-censored data Author: Macro Note: multivariate normal data is in wide format including id, varlist values that are < LOD and need imputed are replaced with LOD varlist: variables need imputation, whether MAR or CAR (coarsening at random) covlist: variables that have no missing data are considered as covariates indexlist: binary variables that identify whether the observations of the corresponding variable in the varlist needs imputed this is useful when some values in the varlist are <LOD but do not need to be imputed; otherwise it is just an indicator for data missing or not noimpute: the value that indexlist variables takes if the observations of the variables in the varlist do not need to be imputed lboundlist: impute values > lbound, . represent no bound LODlist: the limit of detection for the normal data, . represents no LOD iteration-# of iterations for Gibbs sampler to converge ndata-# of multiply imputed data sets for each chain nchain-# of independent Markov chain interval-# thinning parameter of the MCMC chain output ndata imputed data sets from each of the nchain chains: can use ndata data sets from nchain different chains or ndata data sets from a single chain (data set called midata org) varlist, indexlist, lboundlist, lodlist need to have the same dimension this program does not track parameter estimates due to memory constraints */ %macro coarsen(data,id,varlist, covarlist,indexlist, noimpute, lboundlist,lodlist,iteration,ndata,nchain,interval, initialseed); proc iml; * read in data; use &data; read all var {&varlist} into zorg; read all var {&id} into pid; %if &covarlist ne %then %do; read all var {&covarlist} into xcov; %end:

read all var {&indexlist} into indexorg; %end; close &data;

Statistical Analysis Plan Protocol Number: BIO101-CL03

%if &indexlist ne %then %do;

Version Final 2.0, Date: 04JUN2021

```
* sample size;
n=nrow(zorg);
call symput('totaln',left(char(n)));
* dimension of multivariate;
p=ncol(zorg);
call symput('dim',left(char(p)));
* dimension of covariates with no missing data;
%if &covarlist ne %then %do;
pcov=ncol(xcov);
%end;
%else %do;
pcov=0;
%end;
* identify LOD for each variable;
%let li=1;
%do %while (%scan(&lodlist, &li, ' ') ne );
%let lod&li= %scan(&lodlist, &li, ' ');
lodorg=lodorg || &&lod&li;
%let li = %eval(&li+1);
%end;

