%else %do;
x=j(n,1,1)||znew[,index];
%end;
%end; /* this goes with the dim ne 1 loop */
* univariate in varlist;
%if &dim = 1 %then %do;
%if &covarlist ne %then %do;
x=j(n,1,1) | |xcov;
%end;
%else %do;
x=j(n,1,1);
%end;
%end; /* this goes with the dim = 1 loop */
betahat=solve(x`*x, x`*znew[,&parm]);
residual=znew[,&parm]-x*betahat;
* standard deviation of residual variances;
sighat=sqrt((residual`*residual)/(n-p));
* generate a chi-square random variate;
call streaminit(seed);
chisq=rand('CHISQUARE', n-p);
seed=seed+1;
* a random draw of sig jj from inverse chi-square;
sigtilda=sqrt((n-p))*sighat/sqrt(chisq);
* compute Cholesky decomposition;
chol=root(inv(x`*x));
* generate p+pcov random standard normal variates;
bzdev=j(p+pcov,1,0);
call randseed(seed);
call randgen(bzdev, 'NORMAL', 0, 1);
seed=seed+1;
* a random draw of beta_j from multivariate normal;
betatilda=betahat+sigtilda*t(chol)*bzdev;
```

Statistical Analysis Plan Protocol Number: BIO101-CL03 Version Final 2.0, Date: 04JUN2021

Page 64 of 69

```
* compute mu j;
mu=x*betatilda;
* save memory space;
store x residual;
free x residual;
* identify the observed data, including <LOD but do not need to be
imputed;
* note that z is the rearranged original matrix;
%if &indexlist ne %then %do;
iobs=loc(z[,&parm] >lod[&parm] | indorder[,&parm]=&noimpute);
%end;
%else %do;
iobs=loc(z[,&parm] >lod[&parm]);
%end;
zobs=z[,&parm] [iobs];
* identify the MAR in z j;
imar=loc(z[,&parm] = .);
if ncol(imar) > 0 then do;
mumar=mu[imar];
* impute MAR, greater than lbound if there is one;
if lbound[&parm] ^= . then do;
* generate random uniform variates;
uniform mar=j(ncol(imar),1,0);
call randseed(seed);
call randgen(uniform mar, 'UNIFORM');
seed=seed+1;
lmar=(lbound[&parm]-mumar)/sigtilda;
vmar=CDF('NORMAL', lmar, 0,1) + uniform mar # (1-CDF('NORMAL', lmar,
0,1));
zmar=mumar+sigtilda*probit(vmar);
end; /* this goes with the lbound ne . loop */
* impute MAR, if there is no lbound ;
if lbound[&parm] = . then do;
* generate random standard normal variates;
normal=j(ncol(imar),1,0);
call randseed(seed);
call randgen(normal, 'NORMAL', 0, 1);
seed=seed+1;
zmar=mumar+sigtilda*normal;
end; /* this goes with the lbound = . loop */
end; /* this goes with the imar loop */
* no need to impute CAR;
if ncol(iobs)+ncol(imar)=n then do;
* combine the imputed data and update the design matrix;
z&parm.new=(t(iobs)||zobs) // (t(imar)||zmar);
end;
```

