%if (&t=%eval(&iteration-&interval * (&nmi-1)) ) %then %do;
impute=j(n,1,&chain)||j(n,1,mi)||pid||znew;
* rearrange to the original variable order;
impute org=j(nrow(impute),p+3,0);
do m=1 to p;
impute org[,m+3]=impute[,rvarorder[m]+3];
end;
impute org=impute[,1:3]||impute org[,4:p+3];
midata org=midata org//impute org;
mi=mi+1;
%let nmi=%eval(&nmi-1);
* save memory space;
store impute impute org;
free impute impute_org;
%end; /* this goes with the output loop */
```

Statistical Analysis Plan Protocol Number: BIO101-CL03 Version Final 2.0, Date: 04JUN2021

```
%end; /* this goes with the iteration loop */
%end; /* this goes with the nchain loop */
* get variable names for output dataset;
vlist="&varlist";
 %do vi=1 %to &dim;
vname&vi='mi_'+scan(vlist, &vi);
call symputx("varname&vi", vname&vi);
%end;
* note that all variables in the output dataset contained imputation of
missing and left-censored data;
create midata_org from midata_org
[colname={'chain' '_imputation_' "&id"
%do vi=1 %to &dim;
"&&varname&vi"
%end;
 }];
append from midata_org;
quit;
%mend;
* %coarsen(data=walk,
           id=pidn,
           varlist=speed m3 speed m69 speed lod m3 speed lod m69,
           indexlist=complete m3 complete m69 complete m3 complete m69
           noimpute=1,
           covarlist=speed m0,
           lboundlist=0 0 0 0,
           lodlist=. . 0.44 0.44,
           iteration=2000,
           ndata=5,
           nchain=5,
           interval=100.
            initialseed=155504946);
```

Statistical Analysis Plan Protocol Number: BIO101-CL03

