Appendix S2 - Sample SAS Code for PROC MIANALYZE

```
* analyze each imputed dataset;
proc mixed data=midata method=reml;
class pid Arm month;
model speed mi = speed base Arm month Arm*month /solution;
repeated /subject=pid type=un;
lsmeans Arm month Arm*month;
estimate 'PA-HE month 3' Arm -1 1 Arm*month -1 0 1 0;
estimate 'PA-HE month 69' Arm -1 1 Arm*month 0 -1 0 1;
estimate 'PA-HE overall' Arm -1 1;
ods output SolutionF=TEMP1 LSMeans=TEMP2 Estimates=TEMP3;
by imputation ;
run;
* obtain overall significance of the effects;
proc mianalyze parms(classvar=full)=TEMP1 ;
class Arm month;
modeleffects Intercept speed base Arm month Arm*month;
ods output ParameterEstimates=TEMPRESULT1;
run;
* obtain least square means;
proc mianalyze parms(classvar=full)=TEMP2;
class Arm month;
modeleffects Arm month Arm*month;
ods output ParameterEstimates=TEMPRESULT2;
run;
* obtain estimates for the intervention effect;
proc sort data=TEMP3 ;
by label imputation ;
run;
proc mianalyze data=TEMP3;
MODELEFFECTS Estimate;
StdErr StdErr;
by label;
ods output ParameterEstimates=TEMPRESULT3;
run;
```

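### The COVID-19 missing-data sensitivity analysis imputes pandemic dropouts as failed walkers, and its text and code disagree on the ceiling and are written for two arms

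*SAP*

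**What the plan says.** SAP 8.7.6.1 imputes gait speed at M3 and M6/M9 by Bayesian multiple imputation for left-censored data. The rule is: "The 400-m gait speed for the non-completers was imputed subject to the constraint that the value is less than 0.44 m/s". The people it covers are described as follows: "Non-completers include subjects who did not complete the test and discontinued from study, including discontinued due to COVID-19". On grouping it says: "All imputations were performed separately for the two intervention groups".

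Appendix S1 holds the macro that 8.7.6.1 cites. Its header sets a coding convention: "values that are < LOD and need imputed are replaced with LOD". Its example call, which is commented out, imputes four columns with upper limits "lodlist=. . 0.44 0.44", so the first two columns have no ceiling. Values left missing go to a branch headed "impute MAR, greater than lbound if there is one". Appendix S2 models a variable called `speed mi` and uses contrasts such as "estimate 'PA-HE month 69' Arm -1 1 Arm*month 0 -1 0 1".

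Four other places bear on this:

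- The SAP's list of changes from the protocol says 8.7.6.1 was added due to COVID-19 and that the protocol's general provision for extra sensitivity analyses was removed.
- Protocol 7.4 describes COVID-19 discontinuation as consent withdrawal, recorded separately in the eCRF.
- Protocol 9.2 expects non-evaluable withdrawals above 20%.
- SAP 8.7.1 names the comparisons of interest as each dose against placebo.

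**The concern.** A left-censored value is one known to lie below a limit. That describes a participant who tried the walk and could not finish in time. It does not describe someone who withdrew consent in a pandemic, whose walking speed is simply unknown. The text applies the same ceiling to both.

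This is the analysis a reader would use to test the MMRM's missing-at-random assumption. If it disagrees with the MMRM, the plan gives no way to tell whether dropouts were truly doing worse or whether pandemic withdrawals were scored as mobility failure. Two programmers, one following the text and one the example call, could also report different results. The contrast lines as printed do not estimate both quantities of interest.

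**Working it through.** **1. Where the ceiling comes from.** Failing the walk means not covering 400 m in 15 minutes (SAP 8.7.3.2). 400 / (15 × 60) = 400/900 = 0.444 m/s, given as 0.44. The example call uses 5 chains × 5 datasets = 25, which matches the 25 datasets in 8.7.6.1.

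**2. What the ceiling forces.** Exclusion criterion 6 (Protocol 5.3) means an eligible participant walked at 0.444 m/s or faster at screening, so every capped value is a decline. At an assumed baseline of 0.80 the forced loss exceeds 0.80 − 0.44 = 0.36 m/s, which is 3.6 times the 0.10 target.

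For a normal prediction with mean m and SD 0.20 (the SD of change in Protocol 9.2), the mean draw restricted to 0 to 0.44 is m + 0.20 × [φ(a) − φ(b)] / [Φ(b) − Φ(a)], with a = −m/0.20 and b = (0.44 − m)/0.20.

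| m (assumed) | Mean imputed | Change if baseline = m |
|---|---|---|
| 0.7 | 0.347 | −0.353 |
| 0.8 | 0.361 | −0.439 |
| 0.9 | 0.372 | −0.528 |
| 1.0 | 0.380 | −0.620 |

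The untreated decline in Protocol 9.2 is 0.05 m/s.

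**3. How many people.** At 20% loss, 231 × 0.20 = 46.2 people would be placed below 0.44. Applying the 6.9% six-month success-to-failure rate that Protocol 2.2 quotes from LIFE-P gives 46.2 × 0.069 = 3.2. That is a different population and not a rate among dropouts, so this shows scale only.

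**4. Closed-form effect, 77 per arm (231/3), 20% loss in each arm.** Capped dropouts carry no treatment difference, so 0.10 becomes 0.80 × 0.10 = 0.08. The variance in an arm is 0.8 × 0.20² + 0.2 × v + 0.16 × g², where v is the variance of the restricted draw and g is the gap in mean change between completers and dropouts. At m = 0.7, v = 0.0063:

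- Placebo (g = 0.303): 0.0480.
- Drug (g = 0.403): 0.0593.
- Average 0.0536, SD 0.232.

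At m = 1.0 the SD is 0.307. With SE = SD × √(2/77), power is 57% and 37%. Analysing the remaining 61.6 per arm at SD 0.20 gives 79%.

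**5. Simulation of the S1 macro.** From the documents: SD of change 0.20 and 77 per arm. Assumed: baseline mean 0.7 to 1.1 m/s, baseline SD 0.18, M3–M6 change correlation 0.6, and all loss unrelated to walking. Imputation was within arm, with 25 datasets (burn-in 200 and thinning 20, against 2000 and 100 in S1), then ANCOVA at M6/M9 and Rubin's rules at two-sided 0.05 per contrast. There were 300 trials (600 contrasts) per scenario, with Monte Carlo SE at most 0.003. True failures were capped under both methods, so only dropouts differ.

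| Scenario | Ceiling on all dropouts | Dropouts as MAR |
|---|---|---|
| True 0.10, 5% loss | 0.093–0.096; power 61–73% | not shown |
| True 0.10, 10% loss | 0.089–0.091; 38–59% | not shown |
| True 0.10, 20% loss | 0.079–0.082; 22–47% | 0.096–0.099; 73–80% |
| True 0, loss 30% drug, 20% placebo | −0.047 to −0.089; rejects 16–26% | −0.003 to 0.000; about 4% |

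Smaller repeat runs (80 to 200 trials per scenario) gave 0.081 to 0.086 and 22 to 54% power for the ceiling at 20% loss.

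**6. Text against code.** One simulated arm, the same 23 dropouts (mean baseline 0.91), imputed M6/M9 speed:

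| Coding | Mean | Maximum |
|---|---|---|
| Set to 0.44, limit 0.44 (the text) | 0.30 | 0.43 |
| Missing, no limit | 0.81 | 1.39 |
| Missing, limit 0.44 | 0.85 | 1.51 |
| Four-column call, `speed m69` | 0.62 | 1.00 |
| Four-column call, `speed lod m69` | 0.35 | 0.44 |

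Row 3 shows that the limit does nothing unless the value has first been coded at 0.44. Nothing says which column becomes `speed mi`.

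**7. S2 contrasts.** With three arms, unstated coefficients are zero, so the M6/M9 line is arm level 2 minus level 1. In Appendix A's order (175, 350, placebo) that is 350 minus 175. Over all six orders it gives 350−175, 175−350, 175−P, 350−P, P−175 or P−350: always one comparison, never both doses against placebo.

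**The case against.** The best counter-argument is that a sensitivity analysis should depart from MAR. The primary MMRM already assumes MAR, and imputing these dropouts as MAR largely repeats it, so a harsh rule is a real stress test. That stands as a reason to keep a run that caps everyone, labelled as a worst case. It does not justify calling the values left-censored or making it the only such imputation.

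Some points reduce the weight of the code criticism. The S1 call is a commented-out example with both capped and uncapped columns, so the authors may have intended both versions. S2 is headed as sample code. Its pooled fixed-effect solution gives both dose-placebo differences at M6/M9 with standard errors if placebo and M6/M9 are the last levels. Pooled LS means give only point differences. These points stand, but the plan never states the column or the S2 arm order.

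On size, the simulation assumes all loss is unrelated to walking, which favours MAR. The 30% versus 20% imbalance is illustrative, a baseline mean of 1.1 m/s may be high, and power is not what decides a sensitivity analysis. SAP 6.4 also anticipates deviations from exclusion criterion 6, so a few baselines could lie below 0.444.

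Other provisions exist: the adjudication committee in the protocol's governance section (not carried into the SAP), the last-assessment ANCOVA in SAP 8.7.2, and the before/after COVID-19 split in SAP 8.7.6. None of them changes the imputation rule.

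**Conclusion.** The plan is wrong as written on this point and should be corrected, although the primary MMRM is unaffected. Three things follow from the documents alone: the ceiling is the failed-walk speed and is applied to COVID-19 discontinuations; the text and the S1 call do not specify the same imputation; and the grouping statement and S2 contrasts are two-arm.

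The size depends on how many people discontinued and on baseline speed, neither of which the documents give. Attenuation is roughly proportional to loss. An imbalance in loss between arms turns directly into an apparent harm or benefit: in closed form, a 5-point excess in one arm shifts a null difference by 0.015 to 0.028 m/s for baselines of 0.7 to 1.0. If many dropouts in fact left because their walking had worsened, the ceiling would be less wrong and the MAR version too optimistic, which is why the reason for dropout should determine the rule.

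**What to change.** Amend SAP 8.7.6.1 and Appendices S1 and S2 before unblinding:

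1. Apply the bound below 0.44 only to participants who attempted and failed the walk or are documented as unable to do it, by coding those values at 0.44 as the macro header requires.
2. Leave COVID-19 and other administrative gaps missing, so that the macro imputes them as MAR without the ceiling. Make the S1 call match the text and name the column that S2 analyses. If a run capping every dropout is wanted, report it separately as a labelled worst case.
3. State that imputation is done within each of the three arms.
4. Replace the S2 contrast lines with 175 mg minus placebo and 350 mg minus placebo at M6/M9, and state the arm order.

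Optionally, add center and gender to the S2 model to match the primary MMRM.

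The cost is a text and code edit. COVID-19 withdrawals are already flagged in the eCRF (Protocol 7.4), and distance and time are recorded for walks attempted but not completed (Protocol 8.1), so the two groups can be separated without new data.
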